10.2 Adverse Event and Device Deficiency Assessment

10.2.1 Study Reportable Adverse Events

Adverse event definitions are provided in Table 6. To ensure all AEs that are potentially relevant to the SLATE study are collected, the following adverse events will be collected and reported to Medtronic during the study, starting from the time the subject signs the informed consent:

- Device-related AEs
- Procedure-related AEs
- Anesthesia-related AEs
- Epilepsy-related AEs
- All SAEs

Each AE must be recorded on a separate AE eCRF and include a description of the event, the diagnosis, date of event onset, the date the site became aware of the event, diagnostic tests and procedures performed, actions taken as a result of the event, relatedness and severity of the event and the outcome of the event. Subject deaths are also required to be reported. Refer to Section 10.5 for subject death collection and reporting requirements.

Documented pre-existing conditions are not considered AEs unless the nature or severity of the condition has worsened. Unavoidable events listed in Table 6 need not be reported unless the AE worsens or is present outside the stated timeframe post-procedure.

Seizures are inherent to the disease state of the target population of this study and are expected to continue in a portion of subjects after the Visualase procedure. While all seizures will be reported and captured in a seizure diary, they will not be reported as AEs unless there is a worsening in the nature, severity or degree of incidence, according to the Investigator's opinion. Following are examples of seizures that are reportable as AEs:

- Worsening in clinical manifestations (for example, subject began having falls with their seizures which was not previously a component)
- Seizure frequency is increased
- Subject experiences a new seizure type or non-epileptic seizure
- Seizure led to injury or death

Memory and naming decline are established risks following epilepsy surgery involving the temporal lobe. In standard ATL resections, changes in these cognitive scores are expected and consequently are not considered as adverse events unless the magnitude of change exceeds the site investigator's expectations.

This study employs a rigorous battery of neuropsychological tests to better characterize individual change in naming and memory following laser ablation. Changes in these cognitive scores are expected and consequently are not considered as adverse events unless the magnitude of change exceeds expectations by the site investigator.

Similarly, adverse events related to depression and anxiety will also be based on site investigator assessment, and a decline in mood assessment scores alone will not be considered an adverse event.

For AEs that require immediate reporting (see Table 9), initial reporting may be done by completing as much information as possible on an AE eCRF. The remainder of the AE eCRF must be completed as soon as possible.

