7.18 Healthcare Services Utilization

To assess use of healthcare resources specifically associated with epilepsy and the Visualase procedure, healthcare services utilization information will be collected during the Visualase procedure and hospital stay, and for any AEs requiring healthcare resources. Healthcare services utilization related to epilepsy and/or the Visualase procedure includes length of hospital stay, length of stay in ICU, ER visits, AEDs and psychotropic medications, physician office visits, and hospital readmissions.

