Serious Adverse Event (SAE)	Adverse event that a) led to death, b) led to serious deterioration in the health of the subject, that either resulted in 1) a life-threatening illness or injury, or 2) a permanent impairment of a body structure or a body function, or 3) in-patient or prolonged hospitalization, or 4) medical or surgical intervention to prevent life-threatening illness or injury or permanent impairment to a body structure or a body function, c) led to fetal distress, fetal death or a congenital abnormality or birth defect NOTE 1: Planned hospitalization for a pre-existing condition, or a procedure required by the CIP, without serious deterioration in health, is not considered a serious adverse event. (ISO 14155:2011, 3.37)		
Serious Adverse Device Effect	Adverse device effect that has resulted in any of the consequences characteristic of a serious adverse event. (ISO 14155:2011, 3.36)		
Unanticipated Adverse Device Effect (UADE)	Any serious adverse effect on health or safety or any life-threatening problem or death caused by, or associated with, a device, if that effect, problem, or death, was not previously identified in nature, severity, or degree of incidence in the investigational plan or application (including a supplementary plan or application), or any other unanticipated serious problem associated with a device that relates to the rights, safety, or welfare of subjects. (21 CFR 812.3(s))		
	Duration		
Transient	Short-lived, not permanent. For the purpose of this study, adverse events lasting 30 days or fewer are considered transient.		
Prolonged	Continuing, persistent. For the purpose of this study, adverse events lasting more than 30 days but that do not meet the definition of permanent.		
Permanent	Long-lasting, for a year or longer. For the purpose of this study, adverse events not resolved at study exit will be considered permanent.		
Severity			
Mild	A type of adverse event that is usually transient and may require only minimal treatment or therapeutic intervention. The event does not generally interfere with usual activities of daily living. (CDISC)		
Moderate	A type of adverse event that is usually alleviated with additional specific therapeutic intervention. The event interferes with usual activities of daily living, causing discomfort but poses no significant or permanent risk of harm to the research participant. (CDISC)		

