Appendix C: Engel Classification of Postoperative Outcomeⁱ

Class I: Free of disabling seizures^a

- A. Completely seizure free since surgery
- B. Nondisabling simple partial seizures only since surgery
- C. Some disabling seizures after surgery, but free of disabling seizures for at least 2 vears
- D. Generalized convulsions with AED discontinuation only

Class II: Rare disabling seizures ("almost seizure free")b

- A. Initially free of disabling seizures but has rare seizures now
- B. Rare disabling seizures since surgery
- C. More than rare disabling seizures since surgery, but rare seizures for the last 2 years
- D. Nocturnal seizures only

Class III: Worthwhile improvement^c

- A. Worthwhile seizure reduction
- B. Prolonged seizure-free intervals amounting to greater than half the followed-up period, but not <2 years

Class IV: No worthwhile improvement

- A. Significant seizure reduction
- B. No appreciable change
- C. Seizures worse

^aExcludes early postoperative seizures (first few weeks). This exclusion is quantitatively defined as 30 days for this protocol.

b"Rare" is quantitatively defined as ≤2 seizure days per year for this protocol.

^cDetermination of "worthwhile improvement" will require quantitative analysis of additional data such as percentage seizure reduction, cognitive function, and quality of life. This is defined as 80% reduction in seizures for this protocol.

Engel J. Outcome with respect to epileptic seizures. In *Surgical Treatment of the Epilepsies*, edited by J. Engel, Jr. Raven Press, New York. 1987

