Appendix D: Data Monitoring Committee (DMC)

Point	Examples		
DMC will be used	Ongoing oversight for this study will be provided by an independent Data Monitoring Committee (DMC).		
Who will be involved	The DMC will have one statistician, at least one physician specializing in neurosurgery, at least one physician specializing in neurology, and one neuropsychologist. None of the DMC members are participating in the SLATE study. A chairperson from among those members will be identified.		
Responsibility of the DMC	 The DMC will be responsible for the following: Monitoring subject safety through review of aggregate clinical study data and adverse events Acting as an advisory panel on study design, study materials, study conduct, and subject safety issues Ensuring continued scientific validity and necessity, and making recommendations for protocol modifications Investigating root cause of missing data to minimize potential bias (i.e., screen failures, lost-to-follow-up, discontinuation from treatment) Evaluating issues associated with the procedural aspects of the clinical trial (e.g., slow enrollment) and providing recommendations for their resolution 		
Recommendations	The DMC will be advisory to the sponsor. The DMC may provide recommendations for continuation of the study, or early termination due to futility or safety concerns, or early attainment of study objectives. NOTE: Approval to proceed with the study or discontinue the study must be determined by a consensus of the DMC		

A DMC charter will be developed prior to the first subject enrollment.

The DMC will meet (via teleconference or in person) prior to the first subject enrollment to establish procedures for safety data review, chairman appointment, and guidelines for study recommendations. The DMC will meet on a periodic basis to perform data review, including at a minimum, all SAEs and deaths, and will meet more frequently when needed. DMC meetings may consist of both open and closed sessions. Medtronic personnel may facilitate the DMC meetings but will not have voting privileges.

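### Seizures are AEs only if judged worse, and Section 10.2.1 does not name every Table 6 seriousness criterion, so some serious seizures can go unreported as SAEs

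*Protocol*

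**What the plan says.** Protocol Section 10.2.1 lists the events sent to the sponsor from consent onward. The list includes device-, procedure-, anesthesia- and epilepsy-related AEs and all SAEs. Seizures are handled separately: they go into the diary, and "they will not be reported as AEs unless there is a worsening in the nature, severity or degree of incidence", in the investigator's opinion. The list that follows is introduced with "Following are examples of seizures that are reportable as AEs". Its items are changed manifestations, higher frequency, a new or non-epileptic seizure type, and "Seizure led to injury or death".

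Table 6 (Section 10.1) defines an SAE as an adverse event with a serious outcome. One route is serious deterioration in health that results in, among other things, "3) in-patient or prolonged hospitalization". A threat to life and intervention to prevent serious harm are parallel routes.

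Other sections depend on these two rules:

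- Appendix D sets the DMC's periodic data review as "including at a minimum, all SAEs and deaths".
- Appendix F (SAP Appendix 2) admits only Study Reportable AEs to the primary safety endpoint, and only if they are device-, procedure- or anesthesia-related and moderate or severe. Seizure is not among the events that must also be permanent.
- Protocol Section 14.5 and SAP Section 7.9.2 start the efficacy window at day 30. Of early seizures, Appendix C says: "This exclusion is quantitatively defined as 30 days for this protocol".
- Section 7.18 collects utilization for the procedure and hospital stay "and for any AEs requiring healthcare resources".

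**The concern.** Section 10.2.1 tests for worsening before anyone asks whether the seizure was serious. A seizure that fails the first test is not an AE, and something that is not an AE cannot be an SAE as Table 6 is worded. The instruction to collect all SAEs does not clearly rescue it, because the protocol does not say which rule prevails.

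A usual-type seizure that leads to admission, prolongs the procedure stay or threatens life is something a safety committee would expect to see after a brain ablation, and Appendix E lists seizure as a foreseeable event. Under the present text, whether it is seen can depend on how each investigator reads the word worsening, so two sites may report the same event differently. SAP Section 7.10 makes AEs the main source of safety data, so the safety tables would carry any such gap.

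**Working it through.** **The rules in sequence.** Take a seizure of the subject's usual type that meets a Table 6 criterion other than death, causes no injury, and is not judged worse.

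1. Section 10.2.1: no worsening in the investigator's opinion, so not an AE. It goes in the diary.
2. Table 6: an SAE must be an AE, so it is not an SAE.
3. Appendix D: the required review covers SAEs and deaths, so it lies outside the minimum.
4. Appendix F: only Study Reportable AEs qualify, so it cannot enter the primary safety endpoint. The exclusion acts before relatedness is graded.
5. If it falls in the first 30 days, Appendix C and Section 14.5 mean that it does not count against Engel Class I either.

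After day 30 a disabling seizure would count as an efficacy failure, so step 5 is confined to the early period. The diary is only a partial backstop: Section 7.5.1 asks for seizure type and Engel qualifiers, and does not ask for admission or seriousness.

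**The plan's own figure.** The stated power is 89% with 150 treated subjects (Protocol 14.1, SAP 6). The exact lower limit for x successes is the 2.5% quantile of Beta(x, n − x + 1). The smallest x with a limit above 43% is 77 (77/150 = 51.3%, lower limit 43.05%). P(X ≥ 77 | n = 150, p = 0.56) = 0.891, which agrees with the plan. The present point does not alter it.

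**The group exposed.** At the planned 56%, 150 × (1 − 0.56) = 66 treated subjects would not be seizure free. The documents give no rate of admission or other serious outcome for their seizures, so no count of unreported SAEs follows.

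**Room in the primary safety test.** The exact upper limit for x qualifying subjects is the 97.5% quantile of Beta(x + 1, n − x), and it must be below 40%. I take n = 150 treated, because Section 14.4.1 defines the proportion among treated subjects. At x = 47 (31.3%) the limit is 39.4%, which passes. At x = 48 it is 40.1%, which fails.

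The table adds uncounted subjects to those already counted. Both columns are assumptions. Each added subject must have no other qualifying AE, and must have had a seizure that would have been graded related and moderate or severe.

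| Counted | Uncounted | Upper limit as counted | Upper limit if added | Goal if added |
|---|---|---|---|---|
| 15 | 1 | 16.0% | 16.7% | met |
| 15 | 15 | 16.0% | 27.3% | met |
| 30 | 8 | 27.3% | 33.1% | met |
| 30 | 15 | 27.3% | 38.0% | met |
| 45 | 1 | 38.0% | 38.7% | met |
| 45 | 3 | 38.0% | 40.1% | missed |

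If the denominator were instead all 215 enrolled (the safety population of Section 14.3.1), the limit would be 71 subjects (33.0%, upper limit 39.7%), and the reading would be the same.

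**The case against.** The rule is deliberate and has a stated reason: seizures belong to the disease and will continue in some subjects. Several stronger readings that a reader might take from it are not supported.

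- **That serious seizures have no exception.** Injury and death are named, and the list is only of examples. An investigator may treat an admission as a worsening in severity. The escape is possible, not automatic.
- **That every admission for a seizure is a missed SAE.** Table 6 counts hospitalization only where health seriously deteriorated. A precautionary admission would not qualify, and many investigators would call a true serious deterioration a worsening. The gap is the space between these two tests.
- **That early seizures are exempt from safety reporting.** The 30-day footnote affects only the Engel class. A seizure that is reported as an AE in that period, and is related and moderate or severe, can count for safety on the written text of Appendix F (its flow chart is not shown).
- **That epilepsy-related visits and readmissions after discharge are collected only for AEs.** One sentence of Section 7.18 reads that way. But Table 2 and Sections 7.15.1 to 7.15.4 schedule a utilization assessment at each follow-up visit with no AE condition, and Section 7.16 requires one at unscheduled visits.
- **That the DMC would be blind to such events.** SAEs and deaths are its minimum. Appendix D and Section 11.1 also give it aggregate study data, and every seizure is in the diary. What is lost is assured case-level review.

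All of this stands, and it narrows the point. It does not remove the conflict between a rule that reports all SAEs and one that can screen an event out before seriousness is asked.

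**Conclusion.** The point holds in a limited form. Section 10.2.1 and Table 6 together allow a usual-type seizure to meet a seriousness criterion other than injury or death, be judged no worse, and so go unreported as an SAE and outside the DMC's required review. In the first 30 days such an event would count in neither primary endpoint.

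Its frequency is unknown, and any count of missed SAEs would rest on rates that the documents do not give. A reader might infer that the primary safety rate is biased enough to matter, but nothing in the documents shows this. With 150 treated subjects the conclusion changes only when the counted total is already close to 47, for example 45 counted and 3 missed. The harm that can be supported is incomplete and possibly uneven SAE reporting and DMC case review. The change is worth making because it is cheap and removes a contradiction in safety reporting.

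**What to change.** - **Section 10.2.1 and Table 6:** reconcile them by adding one item to the seizures reportable as AEs: any seizure that meets any part of the Table 6 SAE definition, whether or not the investigator judges it a worsening. Routine seizures stay in the diary. No separate grading rule is needed, because Section 10.2.1 already requires relatedness and severity for each AE, and these events could then be assessed under Appendix F like any other.
- **Section 7.18:** reword the sentence that ties collection after the hospital stay to AEs, so that it agrees with the utilization assessments in Table 2 and Sections 7.15 and 7.16 and with the section's own aim of covering epilepsy-related use.

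The cost is two protocol sentences, a few more AE forms and slightly higher SAE counts. The primary safety rate could also rise slightly if any added event qualifies under Appendix F. Sample size, endpoints and tests are unchanged.

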10.2.2 Device Deficiencies

Device deficiency information will be collected throughout the study and reported to Medtronic on a Device Deficiency eCRF. Note that device deficiencies that result in an adverse device effect (ADE) to the subject should be captured as an adverse event only.

Device deficiencies that did not lead to an AE should be reported as Device Deficiencies only and will be evaluated by the Investigator to determine if they could have led to a Serious Adverse Device Effect (SADE) (i.e., if suitable action had not been taken, if intervention had not been made, or if the circumstances had been less fortunate).

10.2.3 Adverse Event Updates and Resolution

For any changes in status of a previously reported AE (e.g., change in actions taken, change in outcome, change in relatedness or severity), an update to the original AE eCRF must be completed. All AEs must be followed until the AE has been resolved, is unresolved with no further actions planned, the subject exits the study, or until study closure, whichever occurs first.

If a subject is being considered for exit from the study prior to study closure, all efforts should be made to continue following the subject until all unresolved procedure-related, anesthesia-related, or device-related AEs, as classified by the Investigator, are resolved or are unresolved with no further actions planned.

At the time of study exit, all AEs with an outcome of "Unresolved, further actions or treatment planned" must be reviewed by the Investigator, and an update to the original AE must be reported. At a minimum, if there are no changes to the description, relatedness, severity, tests and procedures, or actions taken, the outcome must be updated to reflect "Unresolved at time of study closure."

Reportable adverse events that may be deemed transient, prolonged, or permanent in nature (see Appendix F) and are unresolved when the subject exits the study will be considered permanent.

10.3 Adverse Event Classification and Device Deficiency Review and Reporting

All AEs and device deficiencies will be reviewed by a Medtronic representative for completeness and accuracy and will request clarification and/or additional information from the Investigator when necessary.

Adverse events will be classified according to the definitions provided in Table 6.

Medtronic will utilize MedDRA, the Medical Dictionary for Regulatory Activities, to assign a MedDRA term for each AE based on the information provided by the Investigator.

Regulatory reporting of AEs will be completed according to FDA requirements. Refer to Section 10.4 for a list of required Investigator and Medtronic reporting requirements and timeframes. It is the responsibility of the Investigator to abide by any additional AE reporting requirements stipulated by the IRB responsible for oversight of the study.

Appendix E contains the Foreseeable Adverse Event List (FAL), which is a list of AEs related to the system or procedure that have been observed in previous relevant

(epilepsy) studies and may be experienced by subjects. This list may help to assess if an AE is unexpected in nature.

For emergency contact regarding a UADE, SAE and/or SADE, contact a clinical study representative immediately (refer to the study contact list provided in the site's study documents binder/investigator site file or refer to the contact information provided in this CIP).

AEs and deaths will be classified according to the responsibilities and parameters outlined in Table 7 below.

Table 7: Adverse Event Classification Responsibilities

What is Classified?	Who Classifies?	Classification Parameters	
Timing of the Event	Investigator	Pre-operative, intra-operative or post-operative	
Relatedness	Investigator	Procedure Anesthesia Device (Visualase System) Epilepsy	
	Sponsor	Procedure Anesthesia Device (Visualase System) Epilepsy	
	Investigator	Serious adverse event	
Seriousness	Sponsor	Serious adverse event Unanticipated adverse device effect	
Carranita .	Investigator	Mild, moderate, or severe	
Severity	Sponsor	Mild, moderate, or severe	
Diagnosis	Investigator	Based on presenting signs and symptoms and other supporting data	
	Sponsor	MedDRA term assigned based on the data provided by Investigator	
Death Classification	Investigator	SUDEP	

10.4 Adverse Event and Device Deficiency Reporting Requirements

Regulatory reporting of AEs will be completed according to FDA requirements. Refer to Table 8 for a list of required Investigator reporting requirements and timeframes, and of required Medtronic reporting requirements and timeframes.

The Investigator must submit to the Sponsor and to the reviewing IRB a report of any UADE occurring during an investigation as soon as possible, but in no event later than 10 working days after the Investigator first learns of the effect. Medtronic is also required to report these events to the FDA. It is the responsibility of the Investigator to abide by any additional AE reporting requirements stipulated by the IRB responsible for oversight of the study.

10.5 Subject Death

The AE that led to the subject death must be documented on an Adverse Event form as soon as possible after the Investigator first learns of the death. A study exit eCRF must also be completed.

10.6 Product Complaint Reporting

A product complaint is any written, electronic or oral communication that alleges deficiencies related to the identity, quality, durability, reliability, safety, effectiveness or performance of a medical device that has been placed on the market.

Since all device components used in the SLATE study are market-released, product complaint reporting is applicable. This includes when an AE is related to a market-released device during the study. The reporting of product complaints is not part of the clinical study and should be performed in addition to the AE reporting requirements. Refer to FDA regulations (21 CFR Part 803) for reporting requirements.

